10.4.2 Analysis of the Primary Efficacy Endpoint

The primary endpoint is change from baseline in the mean forced vital capacity, measured as the percentage of the age-, height-, gender- and race-adjusted predicted value (FVC-%) over the course of the 18-month treatment period, as reported quarterly (i.e., months 3, 6, 9, 12, 15 and 18). Given that the trajectories of the primary endpoint are expected to differ because of the mechanisms of action of the two treatment modalities, a longitudinal approach incorporating all time points will be employed. Specifically, the endpoint will be analyzed using a linear mixed model with participant-month in the study (3, 6, 9, 12, 15, 18) as the unit of analysis and the change from baseline in FVC-% as the outcome, with terms for baseline FVC-%, treatment group, month, the interaction of month (x) treatment group, and prior MMF therapy (stratification factor: naïve, >0 to \leq 3 months, and >3 months to 6 months), as fixed covariates. Study participant will be treated as a random effect to account for the correlation of outcomes over time within a participant. The model generates adjusted estimates of change from baseline in the FVC-% for each treatment group and month, and an F-test will be used to test the hypothesis that the mean change from baseline during the treatment period differs between the two treatment groups. The model-based adjusted mean change from baseline in FVC-% will be presented graphically by treatment group by study month, with 95% confidence intervals (CIs) provided at each month.

The primary analysis of the primary efficacy endpoint will use the m-ITT analysis set. Appropriate non-linear parametric or non-parametric tests may be applied if the assumptions of the model are not satisfied. Details will be presented in the SAP.

To assess the robustness of treatment effects, a secondary analysis of the primary efficacy endpoint will be performed using the PP analysis set. In addition, two separate *a priori* analyses will be conducted using the model described above with the m-ITT analysis set: one with baseline CT fibrosis scores as a covariate, and one with baseline mRSS as a covariate.

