### 6.3 Randomization and Blinding

This study used randomization and masking as two of the cardinal principles of clinical trials to minimize bias.

*Randomization.* Participants were randomized after all screening assessments were completed and the investigator verified that eligibility criteria were met. Eligible participants were randomized to MMF+PFD or MMF+Plac in a 1:1 manner, stratified by clinical site (pooled into 4 groups) and prior MMF exposure (naïve, >0 to  $\leq$ 3 months, and >3 months to  $\leq$ 6 months). Randomization to the different strata were to be capped if necessary to maintain at least 50% of randomized subjects within the treatment naïve strata (no prior therapy with MMF or DMARD) in order to maintain adequate power. The DCC prepared the randomization schedule, using computer-generated block randomization with the block size(s) known only by the DCC. A secure web-based application was built for use by the coordinators to enter participant information (e.g., participant ID, stratification factor) and to obtain the randomization number. The information was printed and sent and/or emailed directly to the site pharmacists. Participants who withdrew from the study prior to completion of the treatment period were not replaced.

*Blinding.* This is a double-blind study. The study staff (except for select staff at the DCC and Research Pharmacists) and the participant were blinded to the treatment assignment.

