### 8.3 Covariates and Subgroups

Prior MMF therapy (stratification factor: naïve,  $>0$  to  $\leq 3$  months, and  $>3$  months to 6 months) and FVC-% at baseline were included as covariates in the analysis of the primary efficacy endpoint. Several other covariates are incorporated in specific analyses that are denoted in the analysis specifications described below (e.g., secondary analysis of primary endpoint including baseline mRSS as a covariate). No subgroup analyses were planned.

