## 10.1 Primary Efficacy Analysis

The primary endpoint is change from baseline in the mean forced vital capacity, measured as the percentage of the age-, height-, gender- and race-adjusted predicted value (FVC-%) over the course of the 18-month treatment period, as reported quarterly (i.e., months 3, 6, 9, 12, 15 and 18). The primary efficacy analysis tests the null hypothesis that the differences between the MMF+PFD and MMF+Plac is zero. The primary analysis of the primary efficacy endpoint uses the m-ITT analysis set. The endpoint is analyzed using a linear mixed model with participant-month in the study (3, 6, 9, 12, 15, 18) as the unit of analysis and the change from baseline in FVC-% as the outcome, with terms for baseline FVC-%, treatment group, month, the interaction of month and treatment group, and prior MMF therapy (stratification factor: naïve, >0 to  $\leq$ 3 months, and >3 months to 6 months), as fixed covariates. Study participant is treated as a random effect to account for the correlation of outcomes over time within a participant.

The model is summarized below.

$$FVC\%-_{it} = \mu_0 + \mu_1 \text{TRT}_i + \mu_2 \text{MONTH}_{it} + \mu_3 \text{TRT}_i \times \text{MONTH}_{it} + \mathbf{x}_i' \boldsymbol{\beta} + \epsilon_{it},$$

where  $FVC\%-_{it}$  is the change of FVC-% from baseline at time  $t$  for patient  $i$  (that is, FVC-% at time  $t$  - FVC-% at baseline),  $i = 1, \dots, 51$ ;  $t = 1, \dots, 6$  (corresponding to 3, 6, 9, 12, 15 and 18 months).  $\text{TRT}_i$  is treatment group (equal to 1 for the PFD and MMF and 0 for Plac and MMF) for patient  $i$ .  $\text{MONTH}_{it}$  is the study month at time  $t$  for patient  $i$ . Two dummy variables for prior MMF therapy (stratification factor: naïve, >0 to  $\leq$ 3 months, and >3 months to 6 months), and baseline FVC-% for subject  $i$  are included in a vector  $\mathbf{x}_i$  of 3 covariates ( $x_1, x_2, x_3$ ) and associated fixed effects are stored in vector  $\boldsymbol{\beta} = (\beta_1, \beta_2, \beta_3)$ . We assume that residual errors  $\epsilon_{it}$  ( $t = 1, \dots, 6$ ) for subject  $i$  are normally distributed with zero mean and 6x6 general/unstructured variance-covariance matrix.

In the context of the primary analysis of the primary endpoint, we are interested in parameter  $\mu_3$ , representing the trajectories of the primary endpoint adjusted for stratifying variables and baseline covariates.

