The model generates adjusted estimates of change from baseline in the FVC-% for each treatment group and month, and an F-test is used to test the hypothesis that the mean change from baseline during the treatment period differs between the two treatment groups.

The model-based adjusted mean change from baseline in FVC-% will be presented graphically by treatment group by study month, with 95% confidence intervals (CIs) provided at each month.

Analysis	Primary Analysis of the Primary Endpoint: mean FVC-% change from baseline during the treatment period differs between the two treatment groups
Analysis Set	mITT Population
Methods	Linear mixed model for repeated measures with correlated errors
Dependent Variable	Change of FVC-% measured at 3, 6, 9, 12, 15 and 18 months (FVC-% at x months – FVC-% at baseline, where x=3, 6, 9, 12, 15 and 18)
Model	Fixed effects: 
 
• Treatment
 
• Study month
 
• Interaction of treatment and study month
 

	
 
• Stratifying variable: prior MMF therapy with 3 categories
 
• Baseline FVC-%
 

Results	
 
• Estimates of mean change from baseline in FVC-% during the treatment period (slope) by treatment group and treatment difference
 
• 95% confidence interval for treatment estimates and treatment difference
 
• P-value for treatment difference
 

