## 10.2 Secondary Efficacy Analyses

### 10.2.1 Secondary Analyses of Primary Efficacy Endpoint

Several sensitivity analyses are performed to assess how alternative approaches to missing data and model assumptions affect the conclusions of the analysis of the primary outcome:

1. Analysis of the primary efficacy variable as described in section 10.1 is performed using the PP population.
2. Analysis of the primary efficacy variable described in section 10.1 with the m-ITT analysis set except that HRCT fibrosis scores in the lobe of maximal involvement (QLF-LM) at screening is added as a covariate.
3. Analysis of the primary efficacy variable described in section 10.1 with the m-ITT analysis set except that baseline mRSS is added as a covariate.
4. Analysis of covariance (ANCOVA) is used to analyze the change of FVC-% from baseline to month 18 (that is, FVC-% at month 18 - FVC-% at baseline). The model includes the treatment group, baseline FVC-% and prior MMF therapy.
5. In addition to the assessment of the overall trajectory of pulmonary response which integrates the timing of the onset of response and the overall magnitude of effect at 18 months, we evaluate the individual components of this response. This is accomplished by using the linear mixed effects model with same covariates described for the analysis of primary efficacy variable and provide adjusted estimates of change from baseline in FVC-% for each treatment group and treatment difference for each time point (e.g., 3, 6, 9, 12, 15 and 18 months).
6. Descriptive statistics are provided to assess more granular changes in FVC-% by treatment adherence (e.g., premature discontinuation of study treatment prior to 3, 6, 9, 12, 15 and 18 months) in the completers population.

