### 10.2.2 Secondary Efficacy Analyses

The m-ITT analysis set will be used in the analyses of secondary endpoints if not otherwise indicated.

1. The linear mixed model as described for the primary analysis of the primary endpoint is performed to compare the two treatment groups for the change from baseline to 18 months, measured by

3-month intervals, in the following outcomes. The model is adjusted by treatment, study month, interaction of treatment and study month, prior MMF therapy and baseline outcome. For FVC (measured in ml), the model also includes age (measured as a real number and not an integer), height, sex and race (i.e., the same variables used in the percent predicted equations). The model generates adjusted estimates of the change from baseline for each treatment group and month, and an F-test is used to test the hypothesis that the mean change from baseline during the treatment period differs between the two treatment groups. The model-based adjusted mean change from baseline will be presented graphically by treatment group and study month, with 95% confidence intervals (CIs) provided at each month.

- a. Hemoglobin-adjusted DLCOHb-%
  - b. mRSS
  - c. FVC (in ml)
  - d. SGRQ: Total score, Symptoms, Activity, Impacts
2. The linear mixed model as described for the primary analysis of the primary endpoint is performed to compare the two treatment groups for the change from baseline to 18 months, measured at 3-month intervals, in dyspnea. The model is adjusted by treatment, study month, interaction of treatment and study month, prior MMF therapy, and BDI. The model generates adjusted estimates of TDI for each treatment group and month, and an F-test is used to test the hypothesis that the mean change from baseline during the treatment period differs between the two treatment groups. The model-based adjusted mean TDI will be presented graphically by treatment group and study month, with 95% confidence intervals (CIs) provided at each month.

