## 12 Other Analyses

Analyses of the following outcomes will be summarized and allow for further interpretation of the study results. The m-ITT analysis set is used in the analyses.

1. The linear mixed model as described for the primary analysis of the primary endpoint is performed to compare two treatment groups on the change of the PROMIS-29 version 2.0 (in Physical Function, Anxiety, Depression, Fatigue, Sleep Disturbance, Pain Interference, Impact on Social Roles, and a single item on pain intensity) from baseline to month 18, measured by 6-month intervals. The model is adjusted by treatment, study month, interaction of treatment and study month, prior MMF therapy and baseline PROMIS-29. The model generates adjusted estimates of change from baseline in PROMIS-29 for each treatment group and month, and an F-test is used to test the hypothesis that the mean change from baseline during the treatment period differs between the two treatment groups. The model-based adjusted mean change from baseline in PROMIS-29 will be presented graphically by treatment group by study month, with 95% confidence intervals (CIs) provided at each month.
2. A frequency table and bar chart are used to show the frequency distribution of the change of QILD-WL from screening to month 18 categorized in 2% increments. The proportions of participants with better (<-2%), stable ( $\geq -2\%$  to  $\leq 2\%$ ) and worsening ( $>2\%$ ) QILD-WL in each treatment group are also presented.
3. A frequency table is used to evaluate the proportion of participants with a 3% or greater decline from baseline in FVC-% over the 18-month treatment period between the two treatment groups.
4. A frequency table is used to evaluate the proportion of participants with a 5% or greater decline from baseline in FVC-% over the 18-month treatment period between the two treatment groups.
5. Descriptive statistics are used to show the change from baseline to month 6, 12, and 18 in patient global assessment of “overall health” in the past week, overall and in each treatment group.
6. Descriptive statistics are used to show the patient transition questions of global assessment at month 6, 12, and 18 comparing patient’s (i) overall health and (ii) lung involvement to that at the baseline visit, overall and in each treatment group.

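### Pooled site group stratifies the randomisation but is absent from every SAP efficacy model: a small loss of precision if site matters, with no bias in the linear models

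*SAP*

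**What the plan says.** SAP 6.3 and Protocol 10.6.1 both describe 1:1 randomisation "stratified by clinical site (pooled into 4 groups) and prior MMF exposure", the latter in three levels. That gives 4 x 3 = 12 cells.

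The analysis models use one of the two factors:

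- **SAP 8.3:** prior MMF therapy "and FVC-% at baseline were included as covariates in the analysis of the primary efficacy endpoint".
- **SAP 10.1, Model row:** "Stratifying variable: prior MMF therapy with 3 categories". The covariate vector holds two prior-MMF dummies and baseline FVC-%. The text of 10.1 nevertheless speaks of stratifying variables in the plural.
- **SAP 10.2.1 item 4** (month-18 ANCOVA): "The model includes the treatment group, baseline FVC-% and prior MMF therapy".
- **SAP 10.2.2 item 1:** "The model is adjusted by treatment, study month, interaction of treatment and study month, prior MMF therapy and baseline outcome". FVC in ml also adds age, height, sex and race. Items 2 to 4 (TDI, SHAQ, HRCT) and item 6 (logistic) have the same structure, each with its own baseline or screening value.
- **SAP 12 item 1:** "The model is adjusted by treatment, study month, interaction of treatment and study month, prior MMF therapy and baseline PROMIS-29".

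Protocol 10.4.2 also leaves site out of the primary model ("with terms for baseline FVC-%, treatment group, month, the interaction of month (x) treatment group, and prior MMF therapy"), so the two documents agree there. They differ in one place: Protocol 10.4.3.1 lists site among the covariates for dichotomous outcomes, and the SAP's remaining logistic model has no site term. SAP section 14 item f explains the move from logistic regression to frequency tables. It does not explain why site is missing from the logistic model that stays.

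**The concern.** Stratifying on a factor makes the arms similar on it, so the true sampling variance of the treatment difference falls. A model without that factor does not see the reduction and reports a standard error that reflects the full residual variance. Intervals are then a little wide and tests a little conservative. With 51 participants instead of 150, and power of about one third on the visit-averaged contrast, precision available from a variable already on file is worth having. Validity is not at stake.

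The size depends on which contrast is tested. SAP 10.1 says "In the context of the primary analysis of the primary endpoint, we are interested in parameter" mu_3, the treatment-by-month term, but also describes an F-test of the mean change over the treatment period. A site effect that is constant over visits affects the second and not the first.

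**Working it through.** **Inputs from SAP Table 7.1 (Protocol Table 10.5.4).** SDs at months 3 to 18: 4.1, 5.1, 6.2, 6.9, 6.2, 6.2. Correlations at lags of 3 to 15 months: 0.866, 0.834, 0.802, 0.790, 0.780. Cumulative dropout: 6.5, 13, 17, 20, 23, 24%. Scenario 2 differences: 0.75, 1.75, 3.0, 3.125, 3.25, 3.25, with mean 15.125/6 = 2.52. N = 51 comes from the index in SAP 10.1.

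**Reproducing the plan's power.** With a random-intercept model, the 5-df treatment-by-month F-test gives 81.8% (Scenario 1) and 95.9% (Scenario 2) at 75 per arm; the SAP states 82.3% and 95.6%. The visit-averaged contrast gives 56.3% and 80.1%. The stated power therefore matches an interaction test, which a constant site effect does not touch.

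**Expected size by hand.** The SD of the six-visit average is 5.36. If site group explains a share s of that variance, the SD between site groups is 5.36 x sqrt(s), which is 1.2, 1.7 and 2.4 FVC-% points at s = 5, 10 and 20%. Adding site should multiply the SE by about sqrt(1 - s) = 0.975, 0.949, 0.894, before the cost of 3 df. With perfect balance, a nominal 5% test without site rejects when |Z| > 1.96/sqrt(1 - s). At s = 10% the cut-off is 2.07 (level about 3.9%), and at 20% it is 2.19 (about 2.8%).

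**Simulation of the SAP model.** There were 8,000 trials per share, with REML and a 6 x 6 unstructured covariance. Assumed, because the documents do not give them: site groups of 13/13/13/12, a prior-MMF split of 50/25/25, blocks of 4, a site shift constant over visits, dropout at random, and between-participant df. Total variance was held fixed. Visit-averaged contrast, Scenario 2, N = 51:

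| Site share | Type I error without / with site (%) | Power without / with site (%) | Change in power (points) | Change in median SE |
|---|---|---|---|---|
| 0% | 5.5 / 5.5 | 34.3 / 33.6 | -0.7 | +0.4% |
| 5% | 4.4 / 4.8 | 33.4 / 34.8 | +1.4 | -2.2% |
| 10% | 4.3 / 5.3 | 33.6 / 37.2 | +3.7 | -4.9% |
| 20% | 3.5 / 5.0 | 32.8 / 40.6 | +7.8 | -10.5% |

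Differences were taken before rounding. Monte Carlo SE is about 0.24 points for type I error and 0.53 for power; the models with and without site were fitted to the same data sets.

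Change in power on the other contrasts, at shares of 0, 5, 10, 20%:

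- Month-18 difference from the mixed model: -0.4, +0.8, +2.4, +5.5.
- Month-18 ANCOVA: -0.8, -0.3, +0.8, +4.1.
- mu_3: between -0.1 and -0.3 at every share.

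**Sensitivity.**

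- Unequal site groups (20/15/10/6) at a 10% share: visit-average power 35.0 to 38.2%.
- The same share at every visit, 10 and 20%: 34.1 to 37.0% and 32.1 to 39.8%.
- A site effect growing linearly to a 10 or 20% share at month 18: visit average -0.5 and +0.3 points, mu_3 -0.3 and -0.2, month-18 ANCOVA +1.5 and +6.3.
- A random-intercept model instead of the unstructured covariance (1,500 trials): 36.5 to 35.9% (share 0), 35.6 to 35.7% (5%), 36.0 to 38.5% (10%). The SE at 10% goes from 1.552 to 1.488 (-4.1%). The 5-df interaction test is unchanged, and mean estimates with and without site agree to within 0.005.
- A simpler subject-mean ANCOVA: -0.9, +1.6, +3.2 and +8.0 points at 0, 5, 10 and 20%.

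**Logistic model.** Month-18 data are expected for 51 x 0.76 = 38.8 participants. With a control mean of 4.25, a difference of 3.25 and SD 6.2, the proportion above 5 is about 45% on control and 66% on combination. That gives about 21.5 responders and 17.4 non-responders. Adding site raises the coefficients from 4 to 7, so the smaller class per coefficient falls from 17.4/4 = 4.4 to 17.4/7 = 2.5. The simulated chance of separation rises from 2.8% to 5.8%.

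**The case against.** The case for leaving the models alone has real weight:

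- **The named parameter does not gain.** On mu_3 the change is nil or slightly negative. This stands. The gain is confined to the visit-averaged, per-visit and month-18 contrasts, which the SAP also plans.
- **The benefit rests on an unknown.** No site variance is given. Change scores, baseline adjustment and central spirometry quality control (Protocol 7.1.1.1 and 15.1.6) may make it small. At shares of 0 to 2% the three extra parameters cost slightly more than they return. This stands, and it is why the result is a range.
- **A change from baseline starts at zero**, so a site effect that builds up over time is plausible. The mixed model then gains almost nothing and only the month-18 ANCOVA benefits. This stands too.
- **The SAP follows the protocol's primary model**, so the omission there is a choice and not a conflict. This is correct, and it is why the change has to be logged.
- **Sparsity at N = 51.** This is decisive for a log-rank test over 12 cells (51/12, about 4 participants per cell) and a fair reason to omit site from the logistic model. It is not decisive for three main-effect dummies in a linear model.

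Two refinements apply. First, the absence of bias is exact for the linear models only, and under dropout it requires that dropout not depend on site group beyond the modelled terms. In the logistic model the odds ratio is non-collapsible: with an assumed site SD of 0.25 to 0.5 on the logit scale, a conditional odds ratio of 2.0 becomes 1.98 to 1.92 when site is left out. The test of no effect stays valid. Second, the simulation treats 51 as randomised, so about 51 x 0.935 = 48 contribute data, whereas the SAP may mean 51 in the m-ITT set.

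**Conclusion.** The concern holds, and it is minor. One of the two randomisation factors is missing from every SAP efficacy model, and its omission from the logistic model is an unexplained departure from the protocol. For the linear models the consequence is mild conservatism. If site group explains 5 to 10% of variance, the SE of the visit-averaged contrast is about 2 to 5% too large, and about 0 to 4 power points are given up at N = 51. At 20% the loss is about 8 points; at 0 to 2% there is none. These figures assume a site effect constant over visits, Table 7.1's variances and dropout, and the block size and stratum split stated above. mu_3 is unaffected. Its simulated type I error of about 8% is the same with and without site and reflects the unstructured covariance at this sample size without a small-sample correction; it is not part of this point.

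**What to change.** Before unblinding, add the four-level pooled site group used at randomisation as a fixed main effect, without a site-by-month term.

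- **SAP 10.1:** the covariate vector grows from 3 to 6 elements. The Model row becomes: *Stratifying variables: prior MMF therapy (3 categories) and pooled site group (4 categories)*.
- **Same change** in SAP 8.3, 10.2.1 item 4, 10.2.2 items 1 to 4 and section 12 item 1. Items 1 to 3 and 5 of 10.2.1 inherit it from 10.1.
- **Logistic model (10.2.2 item 6):** either restore site as pooled site group, in line with Protocol 10.4.3.1, with a penalised-likelihood fallback if the fit separates, or record in section 14 that it was removed as too sparse.
- **Log-rank test (10.2.2 item 5):** leave it stratified by prior MMF only.
- **Section 14:** log the change and keep the protocol's covariate set as a sensitivity analysis.

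The cost is three degrees of freedom and a logged departure from Protocol 10.4.2. If site explains nothing, the power lost is 0.7 points on the visit average, 0.4 on the mixed model's month-18 difference and 0.8 on the month-18 ANCOVA (about 1.4 for that ANCOVA in a separate simulation). The gain in the mixed model is close to nil if site effects build up over time. The variable is already in the randomisation system. If the sponsor prefers not to change the models, the SAP should at least say why site group is left out and correct the plural in 10.1.
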